State of the question Purpose of the research	
The incidence of cancer in elderly subjects is constantly increasing and improving their management by taking into account their specific needs is one of the objectives of the 3rd cancer plan published in February 2014. New anti-cancer molecules are placed on the market after validation by clinical trials in which elderly subjects are under-represented. There is therefore little data available on the toxicity of these new molecules in elderly patients. Tyrosine kinase inhibitors (TKIs) are indicated in different types of metastatic cancer. Several elements suggest that their toxicity is higher in elderly subjects than in younger subjects: firstly, the pharmacokinetic modifications, drug interactions and more fragile ground, making these toxicities more severe. As the geriatric population is heterogeneous, identifying those subjects most at risk of complications is a crucial issue. It is also a major socio-economic issue, the occurrence of adverse events being the source of a significant additional cost. Our study will evaluate prospectively (cohort) among geriatric (G8 screening score, ADL, IADL, MNA, comorbidities, Performance Status, Get up and Go Test, visual or verbal fatigue scale), biological, pharmacokinetic and pharmacogenomic data, those prognostic factors of severe TKI toxicity in the elderly. The primary objective of this study is to predict severe toxicity (defined as the occurrence of treatment-related adverse events resulting in either discontinuation of more than 3 weeks of treatment, permanent discontinuation of treatment, hospitalisation, or death, i.e. disability or significant or lasting incapacity) of TKIs prescribed in the context of the Marketing Authorisation (MA) in subjects over 70 years of age. The secondary objectives are the rate of non-progression at 6 months (percentage of patients with complete response, partial response or stable disease according to RECIST v1.1 criteria), progression-free survival and the correlation between the pharmacogenomic data and the rate of non-progression at 6 months.

Target population	This study concerns patients aged 70 and over with cancer and treated with a TKI prescribed in the context of the Marketing Authorisation and having signed an informed consent.
Method of observation	
This is a non-interventional, multi-centre, prospective research study with collection of biological samples, in which 250 elderly cancer patients should be included for 24 months at several centres. Once the patient has signed the informed consent, the investigator will collect clinical data before the start of treatment. The investigator or the geriatric nurse will carry out a geriatric evaluation and take an initial blood sample to perform pharmacogenomic analyses. During treatment, the investigator will collect data concerning the type of treatment, toxicities and tumour response. A second blood sample will be taken at the end of the first month of treatment in order to perform pharmacokinetic analyses. A geriatric evaluation will be carried out after 2 months of treatment, either during a telephone interview or in consultation, in order to assess any toxic effects on the patient's general condition.
 
Once treatment has been stopped, patient follow-up data will be collected along with a final geriatric evaluation.

Information collected	The investigator sends to the Institut Bergonié coordinating clinical research assistant (CRA) the inclusion form including the number of the centre, the name of the principal investigator, the first letter of the patient's last name and the first letter of their first name, their age on inclusion, the eligibility criteria, identification of the treatment with TKI, the date of signature of the consent form, along with the date scheduled for the start of treatment. Each patient's personal data will be confidential (data protection act of 6 January 1978 amended by the act of 6 August 2004). On the case report form or any other study document, patients will be identified by their initials (first letter of last name and first letter of first name) and an inclusion number. The investigators should, however, keep a patient identification list in their binder.
Collection of blood samples	As part of this protocol, two blood samples ($2 * 5 \text{ ml} = 10 \text{ ml}$) will be taken for each patient. An initial sample will be taken before the start of treatment upon inclusion and a second sample will be taken at the end of the first month of treatment. Each sample will be anonymised and the following information will appear on the tubes: name of the study, number of the study centre, number of the patient in this centre, date of sample and type of analysis carried out (pharmacokinetics and pharmacogenomics). At the end of the study, blood samples intended for pharmacokinetic analyses will be sent to the pharmacology department of the Bordeaux University Hospital headed by [name], while the samples intended for pharmacogenomic analyses will be sent quarterly (according to the rhythm of inclusions) to the biological resources centre of Institut Bergonié. These samples will be accompanied by the sample routing form on which the date of signing of the sample preservation consent will be indicated. These biological samples will never be linked to nominative data and will be used for research purposes only. Any samples not immediately used will remain stored for future use to help researchers advance their knowledge of oncology and pharmacology.
Study duration	Enrolment period: 24 months Follow-up: 12 months Total duration: 36 months
Information collection methods	After checking the eligibility criteria, and once the informed consent has been signed, eligible patients will be registered centrally at Institut Bergonié by the study coordinator CRA (request by fax from each participating centre). A confirmation of inclusion with an inclusion number will be returned to the investigator. The patient's enrolment in the study will not be effective until the inclusion number has been assigned.
Data analysis method	
Primary endpoints: prediction of severe toxicity (defined as the occurrence of adverse events attributable to treatment resulting in either discontinuation of more than three weeks of treatment, permanent discontinuation of treatment, hospitalisation, death, disability or significant or lasting incapacity) of TKIs prescribed in the context of the Marketing Authorisation in patients aged 70 years or over with cancer.
 
Secondary endpoints: description of toxicities, non-progression rate at 6 months and progression-free survival at one year.
 
Analysis of toxicity: The severe toxicity rate, along with the incidence rates for toxicities grades 1-4 will be reported according to the eligible and evaluable population. These endpoints will be described using frequency, percentage and 95% confidence interval. The toxicity rate will also be reported by subgroup of patients according to the TKI. Prognostic factors of severe toxicity will be evaluated using logistic regression analyses.
 
Non-progression analysis: The non-progression rate at 6 months will be reported according to the eligible and evaluable population, but also by subgroup of patients according to the TKI used. This endpoint will be described using frequency, percentage and 95% confidence interval. Prognostic factors (clinical and geriatric) of 6-month non-progression rates will be evaluated using logistic regression analyses.
 
Analysis of PFS: PFS will be analysed using the Kaplan-Meier method. Median survival will be presented with a 95% confidence interval. Median follow-up will be calculated using the reverse Kaplan-Meier method. Multivariate analyses will be performed according to the Cox proportional hazards model after verifying the risk proportionality assumption.
 
Intermediate statistical analysis: After the inclusion of the first 150 patients, an intermediate statistical analysis will be performed.

Institut Bergonié
Pre-ToxE Protocol

Number of subjects	In this study, we predict that approximately 30% of patients will experience severe toxicity. A population of 250 eligible and evaluable patients will allow us to estimate this proportion with an accuracy of $\pm 5\%$, leading to a 95% confidence interval (24.3%; 35.7%). Subgroup analyses will also be carried out. Subgroups of patients will therefore be defined according to the TKI treatment received (pazopanib, regorafenib, sorafenib, etc.). Assuming that 50 patients are included in a subgroup with a toxicity rate of 30%, the resulting precision will be $\pm 12\%$, for a 95% confidence interval (17.3% ; 42, 7%).
---------------------------	--

STUDY FLOWCHART

		TREATMENT					Follow-up (Beyond 28 days after TKI discontinuation and up to 12 months after TKI initiation)
	SCREENING	Start of treatment D1	Month 1 (D28, ±2 days)	Month 2 (D56, ±2 days)	Month N	Discontinua tion of treatment (within 28 days)	
TKI	Information		MA				
Consultation	X	X	X				X
Eligibility criteria	X						
Informed consent	X						
Demographic data	X						
Height	X						
Weight	X			X			
History of the disease / Medical history / Previous treatments	X						
Performance status (ECOG)	X	X	X				
Biological assessment	X ¹						
Tumour evaluation	X ²		According to the centre's routine practice				
Geriatric evaluation	X ³			X ⁴		X ⁴	
Blood sample for pharmacogenomics		X					
Blood sample for pharmacokinetics			X				
Toxicities			X			X ⁵	
Concomitant treatments			X			X ⁵	
Vital status							X ⁶

1 Within 7 days before D1 of treatment initiation (same day possible): Haematology (CBC, platelets), Biochemistry (sodium, potassium, calcium, magnesium, phosphorus, glucose, LDH, urea, creatinine, ASAT, ALAT, Alkaline Ph., total bilirubin, albumin, total protein), Coagulation (INR, PT, aPTT), Thyroid function (free T4, TSH).

2 Within 4 weeks before D1 of treatment initiation (same day possible).

3 Within 7 days before D1 of treatment initiation (same day possible): G8, Charlson, Cardiovascular diseases, ADL, IADL, ECOG, Get Up and Go Test, verbal or visual fatigue scale, MNA.

4 Evaluation method during a consultation or telephone interview: % weight loss over the past few months, falls, verbal fatigue scale, ADL, IADL.

5 To be collected for 28 days after discontinuation of treatment.

6 Follow-up according to the centre's routine practice.

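### The only pharmacokinetic sample is at D28 and severe toxicity has no start day, so the planned regression can relate toxicity to a concentration that the same toxicity has already altered

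*Combined protocol and SAP*

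**What the plan says.** All references are to the combined protocol and SAP.

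- **Predictors.** The purpose section draws them from geriatric measures together with "biological, pharmacokinetic and pharmacogenomic data, those prognostic factors of severe TKI toxicity in the elderly".
- **PK measurement.** Method of observation provides one: "A second blood sample will be taken at the end of the first month of treatment in order to perform pharmacokinetic analyses". Collection of blood samples allows two samples per patient, the other taken before treatment, so no earlier on-treatment concentration exists. The flowchart puts the PK sample at D28 ±2 days, in a treatment column. The discontinuation column has none.
- **Endpoint.** Data analysis method counts treatment-related events that lead to "discontinuation of more than three weeks of treatment, permanent discontinuation of treatment, hospitalisation, death", or to disability or lasting incapacity. It gives no start day, landmark or fixed window. Flowchart footnote 5 sets only the end of toxicity collection, 28 days after treatment stops.
- **Model.** "Prognostic factors of severe toxicity will be evaluated using logistic regression analyses". No covariate list is given.
- **Population.** Toxicity rates "will be reported according to the eligible and evaluable population". The text available does not say what makes a PK sample evaluable.
- **Records.** "During treatment, the investigator will collect data concerning the type of treatment, toxicities and tumour response". The tube label carries the sample date. No section lists the dose at sampling or the time since last intake.

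**The concern.** A predictor should be measured before the outcome it is meant to predict. Here two components of the outcome are themselves changes in drug exposure. A patient who begins an interruption of more than three weeks in the second week of treatment has already had the event by D28 and is off the drug when the PK sample falls due. If that sample is taken and analysed, the event has influenced the predictor.

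The purpose section gives pharmacokinetic changes as a leading reason to expect more toxicity in older patients, so the PK result will be read with interest. A real exposure effect could be diluted and missed, or an association could appear where there is none.

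Patients with no sample, because they died or stopped for good before D28, raise a different and smaller issue. They drop out of the PK model, which costs events and narrows the question. It adds almost no bias if the timing of toxicity is unrelated to exposure.

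**Working it through.** **1. The plan's own figures.** Number of subjects assumes a 30% rate. For n = 250, 1.96 × √(0.30 × 0.70 / 250) = 0.0568, giving 24.3% to 35.7%. For n = 50, the half-width is 0.1270, giving 17.3% to 42.7%. Both intervals match those printed. Neither uses a concentration, so neither is affected. Expected events: 0.30 × 250 = 75.

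**2. Who is off drug at D28.** An interruption of more than 21 days starting on day s covers at least days s to s + 21. It must include D28 when s ≤ 28 and s + 21 ≥ 28, that is, 7 ≤ s ≤ 28. An earlier start covers D28 only if the interruption lasts longer than the minimum. How far the concentration has fallen depends on the time since last intake and the half-life, which the documents do not give.

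**3. Effect on the odds ratio (OR).** Assumptions, none of them in the documents: standardised concentration N(0,1), 30% events, true OR 1.5 or 1.0 per SD. A share f1 of sampled events and f0 of sampled non-events have a concentration d SD lower. Approximately,

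log OR ≈ [ln(true OR) − f1·d + f0·d] / [1 + 0.3·f1(1 − f1)d² + 0.7·f0(1 − f0)d²].

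With d = 1 and ln 1.5 = 0.405:

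| f1 | f0 | log OR (true 1.5) | OR by formula | OR by simulation | Simulation, true OR 1.0 |
|---|---|---|---|---|---|
| 10% | 0 | 0.305/1.027 = 0.297 | 1.35 | 1.34 | 0.91 |
| 20% | 0 | 0.205/1.048 = 0.196 | 1.22 | 1.21 | 0.83 |
| 10% | 10% | 0.405/1.090 = 0.372 | 1.45 | 1.45 | 1.00 |
| 20% | 10% | 0.305/1.111 = 0.275 | 1.32 | 1.31 | 0.91 |
| 10% | 20% | 0.505/1.139 = 0.444 | 1.56 | 1.56 | 1.09 |

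The direction depends mainly on whether events or non-events are lowered more often. For f1 = 10% or 20% and true OR 1.5, other values of d give:

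- d = 0.5: 1.43 or 1.35 with f0 = 0; 1.49 or 1.41 with f0 = 10%.
- d = 2: 1.20 or 0.99 with f0 = 0; 1.35 or 1.15 with f0 = 10%.

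**4. If few early events are sampled.** Suppose 10% or 20% of events are early, a quarter of these are sampled 1 SD lower, and the rest have no sample. Among sampled events, f1 = 0.025/0.925 = 2.7% or 0.05/0.85 = 5.9%. The formula gives about 1.46 or 1.41, and simulation about 1.45 or 1.40. If no early event is sampled and timing is unrelated to exposure, the OR stays at 1.50 (true 1.5) and 1.00 (true 1.0).

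**5. What a D28 landmark does.** With 10%, 20% or 30% of events early, 67.5, 60 or 52.5 of the 75 remain. If timing is unrelated to exposure, the OR is again 1.50. Power for OR 1.5 (n = 250, two-sided 5%) is 78%, 75% or 71%, against 82% with no early events.

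**The case against.** **Direction.** A reader might infer that the bias must be downwards, so that high concentrations will look protective. The documents do not support this. The endpoint requires an interruption of more than three weeks, so a patient with a shorter interruption or a dose reduction near D28 can be a non-event with a lowered concentration. The third and fifth rows of the table show the bias nearly vanishing or turning upwards. This objection stands, and the direction must be stated conditionally.

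**Number affected.** A reader might also infer that every early event contributes a false low value. The flowchart has the PK sample in a treatment column and none at discontinuation, so a sample after an early permanent stop or death is unlikely. What remains is mainly interruptions running at D28. Against that, Collection of blood samples plans both samples for each patient and makes no exception for an interruption.

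**Silence.** The text is a synopsis with a flowchart. That it does not list the dose at sampling or a PK evaluability rule does not show that these are absent from the case report form or laboratory procedures. If a rule exists, citing it would largely settle the point.

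**Remedy.** The landmark answers a narrower question. If exposure drives early toxicity (odds of an early event doubling per SD, with 14%, 25% or 36% of events early), the landmark OR is 1.38, 1.28 or 1.20 where 1.5 was assumed. This also stands. The landmark estimate describes toxicity after month 1 and should be labelled so.

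**Power.** The study is sized for precision, so the 82% benchmark is this review's and not a target of the plan.

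**Conclusion.** The concern holds in a limited form. As written, the plan allows severe toxicity to be regressed on a concentration drawn after that toxicity and altered by it, mainly in patients who are sampled during an interruption of more than 21 days that began between about D7 and D28.

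Neither the size nor the sign of the bias can be fixed from the documents, which give no toxicity timing and no PK variability. In the 1 SD illustrations, a true OR of 1.5 is estimated at anything from 1.21 to 1.56. The most striking value (0.99) needs 20% of events sampled 2 SD lower and no lowered non-events, and should not be taken as expected.

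The point concerns one family of predictors. A reader might infer that the whole toxicity analysis is compromised, and that does not follow: the severe toxicity rate, its confidence interval and every model without PK are unaffected. It should still be fixed, because the better method is clear and inexpensive.

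**What to change.** State in the analysis plan:

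- **(a) Baseline model without PK**: geriatric, biological and pharmacogenomic factors and TKI, in all eligible treated patients, counting events from D1.
- **(b) Separate landmark PK model**: only patients on TKI and free of severe toxicity on the day of the D28 sample. Count only later events, up to the end of toxicity collection already set in the flowchart (28 days after treatment stops). Include TKI in the model and standardise concentration within TKI.
- **Dating**: date an interruption of more than three weeks from its first day. Otherwise one still running at D28 would pass as event-free and be counted later.
- **Sample rule**: exclude from (b) every sample taken off drug, in events and non-events alike. Account for the dose at sampling where it is recorded.
- **Reporting**: give the numbers of severe toxicities before D28, of missing samples and of samples taken during an interruption. Describe (b) as the association with toxicity after month 1.

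The cost is analysis-plan wording, one extra model and, if the dose at sampling is not already collected, one case report form item. The rule can be fixed before any concentration is known: "At the end of the study, blood samples intended for pharmacokinetic analyses will be sent to the pharmacology department".

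The price is that early events leave the PK model (about 60 of 75 remain if 20% are early, an assumption) and the effect of exposure on early toxicity is not estimated. Some bias from dose reductions before D28 remains if dose is not recorded. For example, if 10% or 20% of the later events are sampled 1 SD lower and no non-events are, the landmark OR is still 1.34 or 1.21 for a true 1.5.

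### The grade 1-4 toxicity incidence has no new-or-worse rule and, for most clinical symptoms, no described pre-treatment grade, so symptoms present before D1 may be counted to an extent nobody can check

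*Combined protocol and SAP*

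**What the plan says.** **Analysis.** In the toxicity paragraph of the Data analysis method section, the plan states: "The severe toxicity rate, along with the incidence rates for toxicities grades 1-4 will be reported according to the eligible and evaluable population". The rates are given as frequency, percentage and 95% confidence interval. The description of toxicities is listed there as a secondary endpoint.

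**Timing of collection.** Method of observation: "During treatment, the investigator will collect data concerning the type of treatment, toxicities and tumour response". In the study flowchart the Toxicities row is blank under screening. Footnote 5 fixes only the end of collection: "To be collected for 28 days after discontinuation of treatment".

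**Attribution.** The severe toxicity endpoint is "defined as the occurrence of adverse events attributable to treatment resulting in either discontinuation of more than three weeks of treatment", or one of the other listed serious consequences. The sentence on grade 1-4 rates does not repeat the attribution wording.

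**What is recorded before treatment.** Method of observation says in general terms that "the investigator will collect clinical data before the start of treatment". The flowchart lists "History of the disease / Medical history / Previous treatments" at screening, with no grading stated. Footnote 1 gives a laboratory panel within 7 days before D1. Footnote 3 gives the geriatric evaluation in the same window: "G8, Charlson, Cardiovascular diseases, ADL, IADL, ECOG, Get Up and Go Test, verbal or visual fatigue scale, MNA". The fatigue scale is the only single-symptom scale in that list.

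**The concern.** A patient aged 70 or over with cancer may start treatment with diarrhoea, pain, oedema or skin changes from the disease, another illness or earlier therapy. If such a symptom is first graded on treatment, the record does not show whether it was already there or at what grade. The plan sets no counting rule to separate the cases, so an unchanged existing symptom can be tabulated as a grade 1-4 toxicity.

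The protocol's opening section gives the scarcity of toxicity data in elderly patients as a reason for the study, so readers are likely to use these rates. An upward shift of unknown size would not show in the confidence intervals, and a larger sample would not remove it. A starting grade that was not recorded at D1 cannot be reliably reconstructed later.

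**Working it through.** **1. The plan's own figure.** The only sizing figure is for severe toxicity: 30% with 250 patients. The half-width is 1.96 × √(0.30 × 0.70 / 250) = 0.0568, giving 24.3% to 35.7%, which matches the Number of subjects section. This interval is not in dispute. The documents give no expected grade 1-4 rate and no symptom prevalence, so what follows rests on assumptions.

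**2. Is there a usable baseline?**

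| Type of toxicity | Pre-treatment record in the documents | Usable as a starting grade? |
|---|---|---|
| Laboratory | Panel within 7 days before D1 | Yes, but no rule links it to the toxicity count |
| Fatigue | Verbal or visual scale within 7 days before D1 | Partly; it is not described as a toxicity grade |
| Other clinical symptoms | Medical history, no grade stated | None described |

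The Concomitant treatments row is also blank at screening, so symptomatic medication is not scheduled there as a substitute.

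**3. Size, on assumptions.** For one clinical symptom, let

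- b = share of patients who have it before D1 (assumed 30%; range 20% to 50%),
- w = probability of new onset in those without it, and of worsening in those with it (assumed 20% for both),
- a = share of existing, unworsened cases that investigators attribute to the TKI (unknown, 0 to 1).

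All new or worsened cases are taken as attributed.

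- New cases: (1 − b) × w = 0.70 × 0.20 = 0.14
- Worsened cases: b × w = 0.30 × 0.20 = 0.06
- New-or-worse incidence: 0.14 + 0.06 = 0.20
- Existing and unworsened: b × (1 − w) = 0.30 × 0.80 = 0.24
- Reported rate: 0.20 + a × 0.24

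| a | Reported, b = 20% | Reported, b = 30% | Reported, b = 50% |
|---|---|---|---|
| 0 | 20% | 20% | 20% |
| 0.25 | 24% | 26% | 30% |
| 0.5 | 28% | 32% | 40% |
| 1 | 36% | 44% | 60% |

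The excess is a × b × (1 − w). At b = 30% it runs from 0 to 24 points. Its maximum is 16 points at b = 20% and 40 points at b = 50%.

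**4. Against sampling error.** For a 20% rate in 250 patients the half-width is 1.96 × √(0.20 × 0.80 / 250) = 0.050. At b = 30% the excess passes 5 points once a exceeds 0.050 / 0.24 = 0.21, that is, once about one in five existing unworsened cases is attributed to the drug.

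**The case against.** The strongest reply is that the word toxicity already implies attribution. Severe toxicity is defined through treatment-related events, and the grade 1-4 rates stand in the same sentence as the severe rate. Read that way, an existing symptom enters only if the investigator misattributes it, and the excess may be zero. This is a fair reading and it is why the range starts at 0. It does not remove the point: the plan does not state attribution for grades 1-4, and without a starting grade the attribution cannot be verified.

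Second, the available text is at synopsis level. The clinical data taken before treatment are not itemised, and the CRF may hold more. So the supportable statement is that no graded symptom baseline is described, not that none exists. The flowchart also needs care. The row reads "Toxicities X X ⁵" and its first mark appears under Month 1, but merged cells may have shifted: the treatment row also shows nothing at D1, when treatment starts. I rely on the blank screening cell and the Method of observation text, not on the D1 cell.

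Three stronger readings are tempting and are not supported:

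- A reader might infer that the primary endpoint is inflated in the same way. It requires both attribution and a serious consequence, so it is less exposed.
- A reader might compare 44% with the 14% of purely new cases and report a 30-point excess. Worsening of an existing symptom is a legitimate toxicity and would be counted under the proposed rule, so the comparator is 20%.
- A reader might infer that grade 1-4 comparisons between TKIs are distorted. The plan reports the toxicity rate, in the singular, by TKI, and sizes a subgroup at 30%, the severe toxicity figure. It is not clear that grade 1-4 rates are broken down by TKI, and the documents do not say that background symptoms differ by tumour. Nor is the target population restricted to metastatic disease; it is described only as patients with cancer.

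**Conclusion.** The point holds as a limitation of the descriptive grade 1-4 incidence, mainly for clinical symptoms other than fatigue. The plan has no new-or-worse rule and describes no starting grade for these symptoms, so existing ones may be counted as far as investigators attribute them to the drug. With 30% prevalence and 20% onset or worsening, both assumed, the overstatement is between 0 and 24 points, and the data as planned cannot show where in that range it falls. The stated sample size and its confidence interval are unaffected. It is worth correcting because the remedy is cheap and the missing information cannot be reliably recovered afterwards.

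**What to change.** 1. In the flowchart, mark the Toxicities row at D1, before first intake. Grade existing symptoms once, on the scale used on treatment.
2. Under Analysis of toxicity, add one sentence: a grade 1-4 toxicity is counted only if it is attributed to treatment and is new or of higher grade than at D1, with the laboratory values from the 7 days before D1 used in the same way.

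The cost is one extra CRF page, at a consultation the flowchart already marks at D1, and one analysis sentence. Reported incidences will be lower.

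### The graded toxicity description stops at grade 4, so fatal toxicities count in the primary composite but have no category in the secondary endpoint that describes toxicities

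*Combined protocol and SAP*

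**What the plan says.** In the combined protocol and SAP, the Analysis of toxicity paragraph under Data analysis method announces the severe toxicity rate and, in the same sentence, the graded output: "incidence rates for toxicities grades 1-4". Grade 4 is the top of the stated range.

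The primary endpoint, in the same section, defines severe toxicity by its consequences. Besides an interruption of more than three weeks, it lists "permanent discontinuation of treatment, hospitalisation, death, disability or significant or lasting incapacity". The statement of purpose at the start of the document also includes death: "permanent discontinuation of treatment, hospitalisation, or death".

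Describing toxicities is the first secondary endpoint listed. For the individual drugs the plan says: "The toxicity rate will also be reported by subgroup of patients according to the TKI". That sentence gives no grade range.

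The supplied text names no grading scale, does not mention a grade 5, and does not set out table layouts. In the study flowchart, toxicities are collected during treatment and for 28 days after it stops, with no limit by grade. Vital status is recorded in follow-up.

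**The concern.** The two outputs do not fit together. A toxicity that kills a patient meets the primary definition, yet no stated grade can hold it. The composite does not make up for this. It is one yes/no result per patient that pools interruption, discontinuation, hospitalisation, death and disability, so it does not say which toxicity was fatal. With an expected rate near 30%, a handful of deaths would also not be visible in it.

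The study is justified by the possibility that TKI toxicity is more frequent and more serious in older patients, for whom data are scarce. A graded safety description with no fatal category errs in one direction only: it can leave out the worst events or show them as less serious than they were.

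**Working it through.** **The plan's own figures.** The inputs come from the Number of subjects section: "approximately 30% of patients will experience severe toxicity" and "A population of 250 eligible and evaluable patients", plus a TKI subgroup of 50 at 30%. With the normal-approximation interval p ± 1.96 × √(p(1 − p)/n):

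- n = 250: 1.96 × √(0.30 × 0.70/250) = 0.0568, giving 24.3% to 35.7%.
- n = 50: 1.96 × √(0.30 × 0.70/50) = 0.1270, giving 17.3% to 42.7%.

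Both stated intervals reproduce. They concern the severe toxicity rate, which includes death, so this point changes neither.

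**Where a fatal toxicity appears under the plan as written.**

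| Output | Includes fatal events? | Identifies the fatal toxicity? |
|---|---|---|
| Severe toxicity rate (composite) | Yes, death is a component | No |
| Logistic regression for severe toxicity | Yes, same outcome | No |
| Graded incidence | No category above grade 4 | No |
| Rate by TKI | Not stated; probably yes (see the objection) | Not stated |

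No row identifies the toxicity that caused a death.

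**How many patients.** The fatal-toxicity rate q is not in the documents, so it is an assumption shown over a range. The expected number is n × q, and the probability of at least one event is 1 − (1 − q)^n.

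| Assumed q | Expected in 250 | P(at least one in 250) |
|---|---|---|
| 0.5% | 1.25 | 71% |
| 1% | 2.5 | 92% |
| 2% | 5.0 | 99.4% |
| 3% | 7.5 | >99.9% |
| 5% | 12.5 | >99.9% |

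At 1% to 3% the expected number is 2.5 to 7.5, or about 3 to 8 patients. Even at 0.5%, at least one such event is more likely than not.

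**Effect per event.** In the full cohort, one patient missing from a toxicity's incidence changes it by 1/250 = 0.4 percentage points. This applies only if the patient has no lower-grade record of the same toxicity. If the toxicity was recorded at grade 3 or 4 before death, the patient is already counted in its incidence and the error is one of grade.

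**The case against.** The strongest reply is that the two outputs are complementary. Severe toxicity is reported next to the graded incidence and counts every treatment-attributable death, and no data are lost because collection has no grade limit. One summary sentence is also not a table specification, and a statistician would probably list the deaths anyway. It stands that no deaths are lost from the primary result and that the table layouts are unknown. But the range is stated as closed, nothing else in the document reports deaths by toxicity, and a plan should not depend on habit to fill that gap.

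Three stronger readings are tempting, and the documents do not support them.

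- **Fatal events are missing from the results by TKI.** A reader might infer this, but the sentence on TKI subgroups has no grade limit. The Number of subjects section sizes that rate as follows: "Assuming that 50 patients are included in a subgroup with a toxicity rate of 30" percent. That is the value given for severe toxicity, which includes death, so the composite is the likelier meaning. If graded incidence is also split by TKI, the same gap would apply there, but the text does not say so.
- **The incidence of severe toxicity is understated.** In this plan severe means having one of the listed consequences. There is no grade-based severe row to understate, and the consequence-based rate is complete for deaths.
- **Each omitted death lowers a toxicity's rate by 2 points in a TKI subgroup.** The arithmetic is 1/50 = 2%. It holds only if graded incidence is split by TKI and the patient is not already counted for that toxicity at a lower grade.

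It is also fair to object that treating death as grade 5 presumes a CTCAE-type scale that the supplied text does not name. The point does not depend on the number: the stated range stops at 4 and no fatal category is mentioned.

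**Conclusion.** The concern holds as a gap in a secondary safety description. The graded incidence ends at grade 4 although treatment-related death belongs to the primary endpoint, so the most serious toxicities can be omitted or shown at too low a grade in the description of toxicities.

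The size is uncertain because it rests on an assumed toxic death rate. The 1% to 3% range is illustrative and is not taken from the documents. The conclusion also assumes that the graded output is produced as worded, with no separate listing of deaths.

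The estimate and confidence interval for severe toxicity, the prognostic model and the sample size all stand. The wording of the rate by TKI is ambiguous and needs clarifying, but it is not shown to leave out deaths.

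**What to change.** Amend the Analysis of toxicity paragraph as follows:

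1. Name the grading scale and its version.
2. Report incidence by toxicity type using the worst grade per patient, including the fatal grade (grades 1 to 5 on a CTCAE-type scale).
3. List fatal treatment-related toxicities by type and TKI.
4. State whether the toxicity rate reported by TKI is the severe-toxicity composite, the graded incidence, or both.

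Do not add a severe category of grades 3 to 5. The plan already defines severe toxicity by consequence. With a second definition, a grade 3 event without any listed consequence would be severe in one table and not in another.

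The cost is a few sentences of text, one extra table column and a short listing. No new data collection should be needed: toxicities are collected without a grade limit, and deaths must already be attributed to treatment or not for the primary endpoint.
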